11.6.4 Safety Evaluation

Safety variables monitored in this study include: AEs; vital signs (systolic and diastolic blood pressure, pulse rate, respiratory rate); spirometry; ECG data; concomitant medication, clinical chemistry, hematology, urine analysis safety panel, BMI, physical examination, respiratory symptoms (cough assessment).

Statistical Analysis Plan Final v 2.0 / 07 April 2014 Confidential

Page 54 of 73

The primary analysis of Safety parameters will be conducted on the Safety population as described in Section 11.1.3 "Descriptive Statistics".

11.6.4.1 Safety Reporting

An exposure emergent AE is defined as an AE that occurs after first product use or that is present prior to first product use and becomes more severe after first product use. All other AEs will not be summarized but provided in listings only.

All AEs occurring from the signing of informed consent will be recorded electronically. The AE listings will include all AEs captured in the database at any time during the study (including those from subjects who were not in the safety population). All AEs occurred after the product test of THS 2.2 or NRT gum will be included in the summary tables. During the screening period prior to the first THS 2.2 or NRT gum product use, only study procedure related AEs will be included in the summary tables.

AEs reported from subjects that have a first product use, but were not randomized will be summarized in a separate sequence: "Exposed but not randomized". The remainder of safety endpoints assessed in enrolled subjects that have a first product use, but were not randomized will be summarized in a separate sequence: "Enrolled but not randomized".

Partial dates will not be imputed, but assumptions will be made as follows to assign to exposure-emergent or not:

Date information	Assign as	
Partial date, e.g.,May2012, or2011. If month/year is the same as, or later than the month and/or year of		
Screening. Partial date, e.g.,May2012, or2011. If month and/or year is earlier than the month and/or year of Screening.		

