12.6.5 Safety Endpoints

In general, all safety data will be listed and tabulated on the safety population by sequence, using the approach described in Section 12.1.3. Safety variables collected during exposure periods will also be reported by product exposure.

AE data will serve as the primary assessment of safety. Other safety variables monitored in this study include: respiratory symptoms (cough assessment, VAS, and Likert scales); vital signs (systolic and diastolic blood pressure, pulse rate, respiratory rate); spirometry; ECG data; clinical chemistry, hematology, and urine analysis safety panel; physical examination; and concomitant medications.

The number and percentage of subjects with AEs and SAEs will be tabulated by system organ class and preferred term. Summaries will also be presented for AEs leading to withdrawal, AEs leading to Death, AEs by relatedness to product exposure, AEs by severity, and laboratory AEs. Tabulations will be performed for both the number of subjects experiencing an event and the number of events. The number and percentage of device events and of subjects with device events will be tabulated by sequence.

The number and percentage of subjects with clinical findings will be tabulated by sequence for laboratory parameters. Shift tables showing change from baseline of clinical findings will be provided for: ECGs, physical examinations, and laboratory parameters (both shifts in

Confidentiality statement: Data and information contained in this document are considered to constitute trade secrets and confidential commercial information, and the legal protections provided to such trade secrets and confidential information are hereby claimed under the provisions of applicable law. No part of this document may be publicly disclosed without the written consent of Philip Morris Products S.A.

Philip Morris Products S.A.	Clinical Study Protocol	Confidential
ZRHR-PK-02-JP	Final 1.0 / 21 June 2013	Page 96 of 122

normal ranges and toxicity grades). Descriptive statistics will be summarized by visit and change from baseline for laboratory parameters, ECG, respiratory symptoms, and vital signs.

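### The SAP's partial-date rule for adverse events is anchored on Screening, although exposure-emergent status is defined by first product use; the effect is probably small

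*SAP*

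**What the plan says.** SAP 11.6.4.1 (Safety Reporting) gives the definition first: "An exposure emergent AE is defined as an AE that occurs after first product use". An event already present that becomes more severe after first use also qualifies. For everything else it says "All other AEs will not be summarized but provided in listings only".

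The next paragraph describes what enters the summaries: "All AEs occurred after the product test of THS 2.2 or NRT gum will be included in the summary tables". For the time before the first THS 2.2 or NRT gum use, "only study procedure related AEs will be included in the summary tables".

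Partial dates are not imputed. Instead, "assumptions will be made as follows to assign to exposure-emergent or not". The table that follows has two rows. One reads "If month/year is the same as, or later than the month and/or year of" Screening. The other reads "If month and/or year is earlier than the month and/or year of Screening". The outcome column of this table is missing from the text we have. We treat that as a loss in reading the PDF and not as a gap in the plan.

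Protocol 12.6.5 states that "AE data will serve as the primary assessment of safety".

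**The concern.** Emergent status is a question about first product use, but the partial-date table answers a question about Screening. The two are different days. Screening takes place from Day -29 to Day -2 (Protocol 9.1), and the first possible exposure is the product test on Day -1 (SAP 6.1). AEs are collected from consent onwards (Protocol 8.2.1), so events can be recorded in the gap.

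Because non-emergent events go to listings only, the date rule also decides whether an event is summarized. A Screening-period event unrelated to any study procedure should stay out of the summaries under SAP 11.6.4.1. Protocol 8.2.2.1 likewise reports only procedure-related Screening events in the study report. With a partial onset date, such an event could enter the summary tables as if it had followed exposure. AE data are the main safety assessment, and Tables 15.2.6.1 and 15.2.6.2.1 are part of the topline results (SAP 12.3).

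**Working it through.** The plan gives no figure to reproduce. The check is a comparison of the rules, one worked example and a count of calendar dates.

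**1. The anchor against the definition.** The SAP uses the same Screening comparison in two other places. In 11.3.4 it separates medical history from concomitant disease, and in 11.6.4.5.1 it separates prior from concomitant medication. Both distinctions are defined relative to Screening, so the anchor is right there. In both tables, same month or later gives the concomitant category and earlier gives the prior category. Carried over to 11.6.4.1, same or later means emergent and earlier means not emergent. That direction is our inference from the parallel tables. The Screening anchor itself is printed.

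**2. How well the rule separates events.** Consent is obtained before or at Screening (Protocol 1.3.1), and conditions found at Screening are recorded as concomitant disease (Protocol 7.4, 8.2.2.1). Hardly any AE can therefore be dated to a month before Screening. Nearly every AE with a partial date falls in the same-or-later row.

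**3. Worked example (assumed dates).** Screening is on 5 September 2013, the product test on 3 October 2013 (28 days later), and the AE onset is recorded only as September 2013.

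- Screening anchor: September is the same month as Screening, so the event is emergent.
- First-use anchor: September is earlier than October, so the event is not emergent unless it worsened after first use.

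All of September precedes exposure, so the second answer fits the SAP's own definition.

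**4. How often the two months differ.** Inputs:

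- Planned study dates are 1 July to 30 November 2013 (Protocol synopsis).
- The lag *g* from Screening to product test is 1 to 28 days (Day -29 or Day -2 to Day -1).
- Day -1 to Day 11 is 12 days, so the latest product test that lets follow-up finish by 30 November is 18 November.
- Assumption: all feasible pairs of Screening date and lag are equally likely.

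For lag *g*, Screening can fall on 141 − *g* dates. Over *g* = 1 to 28 the total is 28 × 141 − 406 = 3,542 pairs.

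Pairs in different months:

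- For *g* = 1 to 18, the last *g* days of each of July, August, September and October count, which is 4*g*. The sum is 4 × 171 = 684.
- For *g* = 19 to 28, the 18 November limit leaves only 18 October dates, so the count is 3*g* + 18. The sum is 3 × 235 + 10 × 18 = 885.

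Total: 684 + 885 = 1,569, and 1,569 / 3,542 = 44.3%.

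| Lag (days) | Pairs in different months | Share |
|---|---|---|
| 1 | 4 / 140 | 3% |
| 7 | 28 / 134 | 21% |
| 14 | 56 / 127 | 44% |
| 28 | 102 / 113 | 90% |

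**5. What the anchor does not change.** When Screening and product test share a month, a month-only date cannot separate before from after, and either anchor gives emergent. A year-only date of 2013 also gives emergent under either anchor. Only events dated to a month that is not before the Screening month but is before the product-test month change class.

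**The case against.** Most of the case on the other side stands, and it limits the point.

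- **Few events are at stake.** Protocol 8.2.1 asks for start and stop dates and times, and Protocol 11.2.1 raises queries for missing data. A wrong count needs an event before exposure, unrelated to study procedures, with a partial onset date. The documents give no count of these.
- **Leaning towards emergent is cautious.** It over-counts rather than hides events, and every AE is listed anyway. This is a fair defence for dates that are truly ambiguous. It does not cover a month that lies wholly before first use, where nothing is ambiguous about onset.
- **The outcome column cannot be read.** This is correct, so the direction of the rule remains an inference. The mismatch between definition and anchor does not depend on it.
- **Worsening after first use.** An event with onset in the Screening month is still emergent if it became more severe after first use. The rule is therefore not wrong for every such event.

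A reader might also infer that 11.6.4.1 contradicts itself, because it bars non-emergent events from the summaries and then admits procedure-related events from before exposure. The documents do not support so strong a reading. The second sentence reads naturally as a specific exception to the general rule. It agrees with Protocol 8.2.2.1 and with the planned procedure-related table (15.2.6.6). What is missing is the word that marks it as an exception. Nor are those events mislabelled as emergent: no AE table title in SAP 11.6.4.2, 12.2 or 12.3 uses that term.

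**Conclusion.** The partial-date table in SAP 11.6.4.1 is wrong as written: it decides emergent status by Screening, while the section defines that status by first product use. No other section corrects it. Under the inferred direction, an event dated only to the Screening month is treated as emergent even when the whole month precedes the product test and the event did not worsen.

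The effect is small. Under an even spread of dates within the planned study period, about 44% of subjects have Screening and product test in different months, so the rule could misfire for them. A reader might take this as the share of AEs misclassified. It is not: it counts subjects in whom an error is possible, and an error also needs a partial date on the right kind of event. No PK endpoint is touched. This is a correction worth making because it costs almost nothing, and it does not put the safety assessment in doubt.

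**What to change.** 1. In the partial-date table of SAP 11.6.4.1, replace Screening by first product use (Day -1 product test). Same or later month/year is then emergent. Earlier is not emergent unless the event worsened after first use. Ambiguous same-month dates stay emergent, so the cautious default is kept.
2. As a clarification, add to the listings-only sentence an exception for study procedure-related AEs before first product use. Show these in a separate row that is not counted as exposure-emergent, and keep them, SAEs included, in Tables 15.2.6.1 and 15.2.6.6. They should not be dropped from Table 15.2.6.1, because it is the only table that SAP 11.6.4.2.1 lists for the SAE summary.

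The cost is a change to the partial-date table, one added clause, one derivation flag and one table row, with no new data. AE counts may become slightly lower. SAP section 3 requires amendments to be final before database lock. If lock has passed, the change belongs in the clinical study report.

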11.6.4.2 Adverse Events

A general summary table of AEs will be presented by sequence and overall, including:

- The number of events and the number and percentage of subjects reporting at least one AE.
- The number of events and the number and percentage of subjects reporting at least one study product –related AE, broken down by product relatedness (related to THS 2.2 / CC, related to NRT gum) and expectedness (expected, not expected).
- The number of events and the number and percentage of subjects reporting at least one AE broken down by severity, including a subject once with worst severity.
- The number of events and the number and percentage of subjects reporting at least one AE leading to any action taken, broken down by action taken related to the product (combining the following items: product use interrupted, product use

Statistical Analysis Plan Final v 2.0 / 07 April 2014 Confidential

2.0 / 07 April 2014 Page 55 of 73

reduced, product use stopped), treatment given (yes, no), study discontinuation, other action taken.

 The number of events and the number and percentage of subjects reporting at least one AE related to study procedure.

Additional summary tables of AEs will be presented by sequence and overall, with a breakdown of the number of events, as well as the number and percentage of subjects reporting each AE, categorized by SOC and PT coded according to the MedDRA dictionary (version 16.0):

- The number of events and the number and percentage of subjects reporting at least one AE.
- The number of events and the number and percentage of subjects with at least one AE related to product exposure and expectedness for investigational product (IP; THS 2.2 or CC) and reference point product (NRT gum).
- The number of events and the number and percentage of subjects with at least one AE leading to study discontinuation.
- The number of events and the number and percentage of subjects with at least one AE related to study procedure.
- The number of events and the number and percentage of subjects with at least one AE by severity (mild, moderate, severe)

If a subject has more than one occurrence of the same AE, the subject will be counted only once within a PT for each sequence, with the worst occurrence based on the presentation (e.g., for presentation by severity = most severe, for presentation by relationship = most related). Missing information on the intensity of AE will be counted as severe.

TFL number	Title
TABLES	
15.2.6.1	Summary of Adverse Events – Safety Population
15.2.6.2.1	Summary of Adverse Events by System Organ Class and Preferred Term – Safety Population
15.2.6.2.2	Summary of Adverse Events by System Organ Class - Safety Population
15.2.6.2.3	Summary of Adverse Events by Preferred Term - Safety Population
15.2.6.3	Summary of Adverse Events by System Organ Class, Preferred Term and Relationship to Study Product Exposure for Investigational Product (THS 2.2 or CC) and Reference Point Product (NRT gum) – Safety Population
15.2.6.4	Summary of Adverse Events Leading to Study Discontinuation by System Organ Class and Preferred Term – Safety Population
15.2.6.5	Summary of Adverse Events by System Organ Class, Preferred Term and Severity – Safety Population
15.2.6.6	Summary of Adverse Events Related to Study Procedure by System

11.6.4.2.2

Statistical Analysis Plan Final v 2.0 / 07 April 2014

Confidential Page 56 of 73

TFL number	Title
	Organ Class and Preferred Term – Safety Population
LISTINGS	90 - 10 - 10 - 10 - 10 - 10 - 10 - 10 -
15.3.6.1.1	Listing of Adverse Events – Screened Population
15.3.6.1.1	Listing of Adverse Events – Screened Population
11.6.4.2.1	Serious Adverse Events (Including Deaths)

A general summary table of SAEs will be presented by sequence and overall, including the number of events and the number and percentage of subjects reporting at least one SAE.

SAEs will be listed in separate listings by sequence.

The data will be presented in the below outputs:

TFL number	Title
TABLES	
15.2.6.1	Summary of Adverse Events – Safety Population
LISTINGS	
15.3.6.1.2	Listing of Serious Adverse Events – Screened Population

Adverse Events Leading to Withdrawal

Summaries will be presented for AEs leading to withdrawal, by sequence and overall as described in Section 11.6.4.2 "Adverse Events".

AEs leading to withdrawal will also be listed in separate listings by sequence.

The data will be presented in the below outputs:

TFL number	Title
TABLES	
15.2.6.1	Summary of Adverse Events – Safety Population
LISTINGS	
15.3.6.1.3	Listing of Adverse Events Leading to Discontinuation – Safety Population

11.6.4.2.3 Laboratory Abnormalities

Laboratory abnormality data will be listed ordered by sequence, product, subject and time point. Details related to the toxicity grading of laboratory abnormalities are available in Section 11.6.4.4 "Clinical Laboratory Evaluation".

TFL number	Title
LISTINGS	
15.3.6.4	Listing of Clinical Chemistry Data, Shift, Changes from Baseline and

Philip Morris Products S.A.	Statistical Analysis Plan	Confidential
Protocol ZRHR-PK-02-JP	Final v 2.0 / 07 April 2014	Page 57 of 73

TFL number	Title
	CTCAE grades – Safety Population
15.3.6.5	Listing of Hematology Data Shift, Changes from Baseline and CTCAE grades – Safety Population
15.3.6.6	Listing of Urinalysis Data Shift, Changes from Baseline and CTCAE grades – Safety Population
15.3.6.1.3	Listing of Adverse Events Leading to Discontinuation – Safety Population

11.6.4.3 THS 2.2 Device Events

All events relating to the THS 2.2 device will be listed for each subject, including event description, device type the event relates to, severity of event, AE relationship, proposed solution and onset/stop dates/times. Device events will be classified according to C54451/Medical Device Problem Codes FDA CDRH.

A summary table of device events will be presented by sequence and overall, including:

- Number of device events and the number and percentage of subjects reporting at least one device event.
- Number of device events and the number and percentage of subjects categorized by severity of device event (minor, major)
- Number of device events and the number and percentage of subjects categorized by AE relationship (related, not related)
- Number of device events and the number and percentage of subjects categorized by event description (Cigarette Holder (CH) stops heating, CH does not charge, CH led blinking red, Smoking experience does not start, electronic malfunction, other)

Device events and inventory will be listed by sequence. Data collected during Screening will be listed but not summarized.

The data will be presented in the below outputs:

TFL number	Title
TABLES	
15.2.6.7	Summary of THS 2.2 Device Events and Malfunctions – Safety Population
LISTINGS	
15.3.6.2	Listing of THS 2.2 Device Events and Malfunctions – Safety Population

11.6.4.4 Clinical Laboratory Evaluation

Table 15 lists the hematology, clinical chemistry, and urine analysis parameters to be assessed in this study.

Statistical Analysis Plan Final v 2.0 / 07 April 2014 Confidential
Page 58 of 73

Table 15: List of Laboratory Safety Parameters

Hematology	Clinical chemistry	Urine analysis
Hematocrit	Albumin	pH
Hemoglobin	Total protein	Bilirubin
Mean corpuscular hemoglobin	Alkaline phosphatase	Glucose
Mean corpuscular hemoglobin	Alanine aminotransferase	Nitrite
concentration	Aspartate aminotransferase	RBC traces
Mean corpuscular volume	Blood urea nitrogen	Protein
Platelet count	Creatinine	Specific gravity
Red blood cell (RBC) count	Gamma-glutamyltransferase	
White blood cell (WBC) count	Fasting glucose	
Differential WBC count:	Lactate dehydrogenase	
 Neutrophils 	Potassium	
 Basophils 	Sodium	
Eosinophils	Total bilirubin	
Lymphocytes	Direct bilirubin	
Monocytes	Total cholesterol	
Monocytes	Triglycerides	

Any clinical safety laboratory test result that is outside of the normal reference range will be reviewed by the PI and assessed for clinical relevance. If the PI considers the abnormal result to be of clinical relevance, then it must be recorded as a concomitant disease at Screening, or if not present at Screening, as an AE during the study. If the condition worsens from screening to after product-use it will be recorded as an AE.

The grading scheme used in the Common Terminology Criteria for Adverse Events and Common Toxicity Criteria [CTCAE] version 4.03) will be used by the PI to assess abnormal laboratory AEs. These CTCAE grades will be derived programmatically in the creation of the datasets.

Laboratory data will be summarized and listed at baseline (Admission, Day -1) and at discharge (Day 4 or at the day of withdrawal), together with changes from baseline. The number and percentage of subjects with normal results, high/low results and abnormal clinical result (as defined by PI comment) will be tabulated for laboratory parameters.

Listings for the clinical laboratory data will include the following information: normal/high/low (with respect to the reference range), abnormal clinically relevant (as defined by the PI comments), the PI comments, the change from baseline and the CTCAE grade. Only CTCAE grades greater than zero will be presented.

TFL number	Title
TABLES	
15.2.6.10	Summary of Clinical Chemistry Parameters - Safety Population
15.2.6.11	Summary of Hematology Parameters - Safety Population
15.2.6.12	Summary of Urinalysis Parameters – Safety Population

Philip Morris Products S.A.	Statistical Analysis Plan	Confidential
Protocol ZRHR-PK-02-JP	Final v 2.0 / 07 April 2014	Page 59 of 73

TFL number	Title
LISTINGS	
15.3.6.4	Listing of Clinical Chemistry Data, Shift, Changes from Baseline and CTCAE grades – Safety Population
15.3.6.5	Listing of Hematology Data Shift, Changes from Baseline and CTCAE grades – Safety Population
15.3.6.6	Listing of Urinalysis Data Shift, Changes from Baseline and CTCAE grades – Safety Population

11.6.4.5 Vital Signs, Physical Findings and Other Observations Related to Safety

11.6.4.5.1 Prior and Concomitant Medication

Prior medication is defined as any medication that started and ended prior to Screening. Concomitant medication is defined as any medication starting on or after Screening. Medications that started prior to Screening and are ongoing at Screening are considered as concomitant.

All medications will be listed by sequence using PT and Anatomical Therapeutic and Chemical (ATC) codes (World Health Organization - Drug Dictionary Enhanced [WHO-DDE] Q1 2013). A flag will be presented on the listing indicating whether the medication is prior or concomitant. Partial dates will not be imputed, but assumptions will be made as follows to assign to either prior or concomitant:

Date information	Assign as
Missing stop date	Concomitant
Partial date, e.g.,May2012, or2011. If month/year is the same as, or later than the month and/or year of	Concomitant
Screening. Partial date, e.g.,May2012, or2011. If month	Prior
and/or year is earlier than the month and/or year of Screening.	

Prior and concomitant medications will be listed by sequence. Concomitant medications will be summarized for the Safety population showing the number (%) of subjects who used the medication at least once by sequence and by ATC 1st and 2nd levels medical term and by preferred drug name. Listings will be provided by sequence and will display original dates (no imputation).

TFL number	Title
TABLES	
15.2.6.8.1	Summary of Prior Medication by Anatomical Therapeutic Classes
	(ATC) 1 and 2 – Safety Population

Philip Morris Products S.A. Statistical Analysis Plan Confidential Protocol ZRHR-PK-02-JP Final v 2.0 / 07 April 2014 Page 60 of 73

TFL number	Title
15.2.6.8.2	Summary of Prior Medication by Preferred Drug Name - Safety
	Population
15.2.6.9.1	Summary of Concomitant Medication by Anatomical Therapeutic
	Classes (ATC) 1 and 2 – Safety Population
15.2.6.9.2	Summary of Concomitant Medication by Preferred Drug Name –
	Safety Population
LISTINGS	ii.
15.3.6.3	Listing of Prior and Concomitant Medication – Safety Population

